#### TheraGauze/Tobramycin creation

1. TheraGauze commercial preparation will be dehydrated in the factory and spiral dye to yield a 17 cm strip of TheraGauze of uniform width. After cutting the dry TheraGauze will be packaged and sterilized by gamma radiation. This follows all of the current steps of manufacturing only adding dehydration and cutting steps.
2. Dried TG packages will be provided to the Sentara Norfolk General Hospital (SNGH) Emergency Department (ED).
3. Commercial 10 ml vials of tobramycin ophthalmic solution (3 mg/ml) for human use will be provided by the SNGH pharmacy and stored in the temperature monitored med room in the SNGH ED. Each vial will be opened only once and then discarded.
4. After randomization has been determined, a new 10 ml vial of tobramycin ophthalmic solution will be opened and added to newly opened TG in a sterile dish by the study coordinator and allowed to rehydrate to saturation (5 minutes). Maximal saturation of the 17 cm TheraGauze strip is achieved with only 7 ml of solution.
5. The wound will be packed with the TheraGauze/tobramycin strip and any excess length will be cut off, measured and discarded.

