#### Methods:

*Study Population:*

Subjects from the Hampton Roads region of southeastern Virginia will be recruited from the hospital emergency department site staffed by EVMS physicians at Sentara Norfolk General Hospital.

*Study Size:*

We anticipate screening 200 patients in order to enroll and randomize 100 subjects. Subjects will be randomized 2:1 to the TheraGauze+tobramycin or iodoform wick/ plain cotton wick, respectively. We anticipate 50 participants completing the study. The 50% retention rate is typical for emergency department populations.

*Subject Eligibility:*

Inclusion criteria:

- Ages  $\geq 18$  to  $\leq 65$  years at time of enrollment
- Subject has skin abscess (furuncle) requiring incision and drainage
- Erythema surrounding abscess
- Induration of  $\geq 2$ cm in maximal diameter
- Fluctuance or purulent head evident
- Tenderness at abscess
- No or mild fever  $\leq 38.5^{\circ}\text{C}$
- Male or female
- Ability to read and understand the English language at a level sufficient to provide informed consent and comply with study requirements
- Subject is willing and able to comply with all study requirements

Exclusion criteria:

- Systemic illness or deep-seated infection requiring inpatient admission (i.e. hypotension, tachycardia, or tachypnea)
- Deep seated infection requiring referral to surgery
- Subject requires intravenous antibiotics for suspicion of systemic spread of infection (i.e. suspicion of bacteremia)
- Extensive cellulitis extending  $> 6$ cm beyond the area of induration
- Fever  $> 38.5^{\circ}\text{C}$
- Allergy to any aminoglycoside antibiotic, sulfamethoxazole-trimethoprim, doxycycline, clindamycin.
- An underlying medical condition that impairs normal immune function (e.g. AIDS, cancer, diabetes, lupus, rheumatoid arthritis, organ or marrow transplantation, ulcerative colitis, Crohn's disease)
- Subject is pregnant or breastfeeding and/or a woman of childbearing potential who is not surgically sterile, not at least 2 years postmenopausal, or does not practice contraception methods, unless sexually abstinent for the duration of the study.
- Subject has any medical or psychiatric condition, in the opinion of the investigator, could jeopardize the subject's health or compromise the subject's ability to participate in the study.
- Subject has prior treatment with antibiotics in the preceding 7 (seven) days.

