- Currently taking or has taken oral or injection steroid medication (e.g. prednisone or Medrol Dosepak) in the past 30 (thirty) days

- Injection medications (Remicade, Humira, Cimzia, Simponi) other than vitamin (B6)
- Currently taking or has taken immune suppressing medications (e.g. methotrexate, Prograf, CellCept, Rapamune) in the past 30 (thirty) days
- Currently taking or has taken medications to treat cancer in the past 30 (thirty) days
- Subject is currently participating or has participated within the last two months in any study of an investigational drug or device.

*Recruitment and Retention:*

Subjects who present to Emergency Department setting for care of skin abscess requiring incision and drainage will be approached by on-site Study Coordinators for enrollment. The study coordinators and physician investigators are trained in obtaining informed consent. The potential subjects will be able to discuss participation with any family-member present, but due to the need for prompt treatment, the subject will need to make a decision regarding participate at the time of the Emergency Room visit. Upon meeting eligibility criteria and willingness to participate, subjects/LARs will provide informed consent. Complete demographic information to include residential and telephone contact information will be obtained. Prior relevant medical history and usual primary care contact information will also be collected. A medical information release will be obtained from the subject so that outcomes data can be collected related to additional unscheduled visits or adverse events cared for outside the emergency department setting.

*Women and minority participation:*

Adults up to 65 years of age will be enrolled regardless of gender and minority status as long as they are fluent in English.

*Randomization:*

A study subject identification number will be assigned. Subjects will then be sequentially randomized to one of two treatment arms upon enrollment in a 2:1 ratio, using a prepared list. Each subject's name will be recorded on the list next to his/her assigned subject number and randomization. For example, the first subject enrolled will be randomized to Treatment 1; the next enrolled subjects will be enrolled to Treatment 1; the third subject to Treatment 2. The fourth subject will be randomized to Treatment 1 and so on.

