**Study Treatments**

Visit 1 - Day 1:

- Informed consent will be obtained from subject.
- Review of Eligibility Criteria (Inclusion/Exclusion)
- Randomization to Treatment Arm
- Contact Information to include phone number(s), address, and primary care provider information will be collected.
- Treatment and discharge with instructions to return to the ED for reevaluation per routine care. The typical schedule is for the patients to return to the ED 2 days after initial wound care (Study Day 3 -1/+2).

The following information will be collected and recorded on a hard copy Case Report Form at this visit.

- Subject ID number
- Demographics

- Date of visit
    - Age in years and months at time of enrollment
    - Race (white, non-white)
    - Ethnicity (Hispanic or non-Hispanic)
  - Medical history
    - Chronic medical conditions:
      - \_\_\_\_\_
      - \_\_\_\_\_
      - \_\_\_\_\_
      - \_\_\_\_\_
    - Concomitant Medications
      - \_\_\_\_\_
      - \_\_\_\_\_
      - \_\_\_\_\_
      - \_\_\_\_\_
    - Allergies to medications
      - \_\_\_\_\_
      - \_\_\_\_\_
      - \_\_\_\_\_
  - Characteristics of symptoms and history
    - Duration of symptoms (number of days)
    - Fever > 38.0°C duration? (y/n, record number of days febrile at home prior to ED visit)
    - Fever > 38.0°C in ED? (y/n, record temp)
    - Spontaneous drainage (y/n)
    - Prior skin abscess (y/n)
    - Immediate family history (parent, sibling, child) of skin abscess (y/n)
  - Abscess characteristics
    - Erythema at widest diameter (mm)
    - Abscess induration at widest diameter (mm)
    - Abscess location (e.g. trunk, extremity, buttocks, perineal, axilla, head/neck)
  - Procedure information
    - Diameter of wound after incision (mm)
    - Treatment Arm:
      1. Anti-microbial TheraGauze (TheraGauze/tobramycin)
      2. Iodoform wick/ plain cotton wick
    - Length of packing used (mm)
  - Laboratory Assessments – Per standard clinical care the abscess contents will be sent for routine Gram stain, bacterial culture and susceptibility testing as dictated by the patient's insurance and ED policy.
    - Obtain results when available
  - If patient is to receive iodoform wick/plain cotton wick then the care provider will have the option of prescribing a p.o. antibiotic, as is frequently done in these clinical settings. The following oral antibiotic choices are available for subjects in the control arm only:
    - Bactrim (TMP/SMX)
    - Vibramycin (doxycycline)

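### Allocation is described only as a prepared list with the example order 1, 1, 2, 1 and so on; with no random generation or concealment stated, the next arm could be foreseen

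*Combined protocol and SAP*

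**What the plan says.** The Design section of the Methods labels the trial prospective and randomized. The Randomization paragraph is the only place that says how: "Subjects will then be sequentially randomized to one of two treatment arms upon enrollment in a 2:1 ratio, using a prepared list". It then gives an order: "For example, the first subject enrolled will be randomized to Treatment 1; the next enrolled subjects will be enrolled to Treatment 1; the third subject" goes to Treatment 2, and "The fourth subject will be randomized to Treatment 1 and so on". Treatment 1 is TheraGauze with tobramycin; Treatment 2 is the iodoform or plain cotton wick.

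On handling of the list, the paragraph says: "Each subject's name will be recorded on the list next to his/her assigned subject number and randomization".

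Other relevant places:

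- **Recruitment and Retention:** eligible patients "will be approached by on-site Study Coordinators for enrollment".
- **TheraGauze/Tobramycin creation, step 4:** once the arm is known, the tobramycin is added to "newly opened TG in a sterile dish by the study coordinator and allowed to rehydrate to saturation".
- **Study Size:** "We anticipate screening 200 patients in order to enroll and randomize 100 subjects", in a 2:1 ratio, with 50 expected to complete.
- **Study Treatments, Visit 1:** consent and eligibility review are listed before randomization.
- **Statistical Analysis Plan:** nothing on allocation.

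No section says how the list was generated, who prepared or holds it, whether future rows are visible, or what conceals them.

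**The concern.** Randomization protects a comparison only if the person deciding whether to enrol a patient cannot tell which arm comes next. The printed order, continued, is a repeating cycle with no random element. Under such a cycle nobody needs to see the list: coordinators approach patients and also prepare the TheraGauze, so they know what the last patients received. Listing consent and eligibility review before randomization does not help if the next arm is already predictable.

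There is also a plausible motive to select. The two packings look different, no blinding is described, and only control patients may be prescribed oral antibiotics. Staff could, without any ill intent, hold back patients with worse abscesses from one arm's slots.

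The between-arm comparison is at stake. The primary endpoint is safety and side effects compared with standard of care, and the Statistical Analysis Plan adds equivalence tests. The Adverse Reaction paragraph under Assessment of Safety accepts that increasing pain or redness may reflect either infection or local toxicity. An imbalance in abscess severity could therefore be read as a difference in toxicity.

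**Working it through.** **1. The plan's own figures.** 100 randomized × 50% retention = 50 completers, as stated. Extending the cycle 1, 1, 2 over 100 positions makes every third subject a control: 33 control and 67 TheraGauze. That fits the stated 2:1, so the printed order is consistent with a fixed rotation.

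**2. Does the example prove a rotation?** No. The sequence 1, 1, 2, 1 could open a random list:

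- simple 2:1 randomization: (2/3)³ × (1/3) = 9.9%
- permuted blocks of 3: (1/3) × (2/3) = 22.2%
- permuted blocks of 6: (4/6)(3/5)(2/4)(2/3) = 13.3%

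The text neither establishes a rotation nor rules one out.

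**3. How foreseeable is the next arm to someone who remembers past assignments?** The block sizes are assumptions, since the documents give none. For blocks of 3, the orders 112, 121 and 211 have 1, 1 and 2 forced positions, so 4/9 = 44.4% are certain. Best-guess accuracy is (2/3 + 2/3 + 1)/3 = 7/9 = 77.8%.

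| Scheme | Guessed correctly | Known for certain |
|---|---|---|
| Literal 1-1-2 cycle | 100% | 100% |
| Blocks of 3, size known | 77.8% | 44.4% |
| Blocks of 6, size known | 74.4% | 28.9% |
| Blocks of 9, size known | 72.8% | 21.4% |
| Sizes 3, 6 and 9 mixed, set known (simulated, 2,000 lists of 100) | 73.7% | not computed |
| Simple 2:1, always guessing TheraGauze | 66.7% | 0% |

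**4. What selection could do (hypothetical; no input comes from the documents).** Let a share h = 0.30 of patients be at higher risk, with worsening pain or redness in 30% of them and 10% of the rest. The rate without selection is 0.30 × 30% + 0.70 × 10% = 16.0%. If a fraction q of higher-risk patients is passed over for one arm's slots, that arm's higher-risk share becomes h(1−q)/[h(1−q) + 1−h]. The number passed over is slots/(0.3(1−q) + 0.7) − slots.

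| q | Higher-risk share | Event rate | False difference (points) | Passed over, 67 slots | Passed over, 33 slots |
|---|---|---|---|---|---|
| 0.25 | 24.3% | 14.9% | 1.1 | 5.4 | 2.7 |
| 0.50 | 17.6% | 13.5% | 2.5 | 11.8 | 5.8 |
| 0.75 | 9.7% | 11.9% | 4.1 | 19.5 | 9.6 |

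With h from 0.2 to 0.4, a higher-risk event rate from 20% to 40%, the other rate at 10% and q from 0.25 to 0.75, the false difference runs from 0.4 to 7.7 points. Its sign depends on which arm is avoided.

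**5. Against sampling error, at a 16% event rate.**

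- All randomized: SE = √[0.16 × 0.84 × (1/67 + 1/33)] = 7.8 points; 90% CI half-width 1.645 × 7.8 = 12.8 points.
- Completers split 33 and 17: SE = 10.9 points; half-width 18.0 points.

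A shift of this size would be hard to see in the outcome results.

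**The case against.** - **The order is offered as an example.** The paragraph also uses the word randomized, so a proper list may exist and merely be undescribed. This stands to the extent that deterministic allocation is not proven. It does not rescue the plan: the example is the only rule given, following it yields a rotation, and the alternative reading still has no generation method or concealment.
- **This is a Phase I pilot whose control arm is meant only to supply some side-effect data, with mostly descriptive analysis.** That is fair as to ambition. But the primary endpoint is comparative, equivalence tests are planned, and the Research Monitor is to look for superiority or inferiority between arms.
- **The Adverse Reaction paragraph separates infection from toxicity in part.** More purulent drainage, or new fluctuance needing another drainage, counts as progression, and an investigator judges ambiguous pain or redness. This narrows the mechanism without removing it. Systemic side effects such as diarrhea or nausea have no stated link to abscess severity.
- **Baseline severity is recorded and eligibility limits its range.** Erythema, induration, symptom duration, fever and prior abscess are collected at Visit 1, so an imbalance in these could be examined. Selection on unrecorded features could not.
- **The 100 patients screened but not enrolled may be ineligible or may refuse.** Correct: that figure is only an upper limit on the room for selection.
- **Physicians and Emergency Room staff identify patients before coordinators do** (Roles of Research Team Members). True, but coordinators still explain the study and may take consent, and staff who treat patients in an open trial also see past assignments.

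**Conclusion.** The concern holds and must be fixed. A trial presented as randomized gives one allocation rule; followed literally, that rule makes all 100 assignments predictable. If the order is only illustrative, generation and concealment are still missing, and predictability depends on a scheme nobody has stated: 78% with blocks of 3, if those were used.

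The size of any resulting bias is unknown. The 1.1 to 4.1 points (0.4 to 7.7 across the wider range) rest wholly on assumed risks and assumed selection, and the rating does not depend on them. The rating rests on the missing method. The finding is one of exposure to bias in either direction, not evidence that selection took place.

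**What to change.** Replace the Randomization paragraph and delete the 1-1-2 example. The new text should state that:

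- the statistician computer-generates a 2:1 list in permuted blocks of randomly varied size, with the sizes kept out of the protocol and unknown to enrolling staff;
- the list is concealed in sequentially numbered, opaque, sealed envelopes or a password-protected allocation table, with a named role outside enrolment controlling it;
- each assignment is revealed only after consent and eligibility are documented, keeping the order already set for Visit 1;
- the log linking names to subject numbers is kept apart from the allocation list.

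If a random, concealed list already exists, describing it and removing the example resolves the point.

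**Cost.** One paragraph, a short list-generating program, and envelopes or a controlled table. No extra patients are needed, though someone outside enrolment must control access. The final split may miss exact 2:1 by a few subjects. Varied blocks reduce guessing without removing it: about 74% correct for someone who knows the set of sizes (3, 6 and 9 in the calculation) and remembers every assignment. Simple 2:1 randomization would lower that to 67%, but the TheraGauze count would then vary with a standard deviation of √(100 × 2/3 × 1/3) = 4.7 subjects.

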**Study Treatments**

Visit 1 - Day 1:

- Informed consent will be obtained from subject.
- Review of Eligibility Criteria (Inclusion/Exclusion)
- Randomization to Treatment Arm
- Contact Information to include phone number(s), address, and primary care provider information will be collected.
- Treatment and discharge with instructions to return to the ED for reevaluation per routine care. The typical schedule is for the patients to return to the ED 2 days after initial wound care (Study Day 3 -1/+2).

The following information will be collected and recorded on a hard copy Case Report Form at this visit.

- Subject ID number
- Demographics

- Date of visit
    - Age in years and months at time of enrollment
    - Race (white, non-white)
    - Ethnicity (Hispanic or non-Hispanic)
  - Medical history
    - Chronic medical conditions:
      - \_\_\_\_\_
      - \_\_\_\_\_
      - \_\_\_\_\_
      - \_\_\_\_\_
    - Concomitant Medications
      - \_\_\_\_\_
      - \_\_\_\_\_
      - \_\_\_\_\_
      - \_\_\_\_\_
    - Allergies to medications
      - \_\_\_\_\_
      - \_\_\_\_\_
      - \_\_\_\_\_
  - Characteristics of symptoms and history
    - Duration of symptoms (number of days)
    - Fever > 38.0°C duration? (y/n, record number of days febrile at home prior to ED visit)
    - Fever > 38.0°C in ED? (y/n, record temp)
    - Spontaneous drainage (y/n)
    - Prior skin abscess (y/n)
    - Immediate family history (parent, sibling, child) of skin abscess (y/n)
  - Abscess characteristics
    - Erythema at widest diameter (mm)
    - Abscess induration at widest diameter (mm)
    - Abscess location (e.g. trunk, extremity, buttocks, perineal, axilla, head/neck)
  - Procedure information
    - Diameter of wound after incision (mm)
    - Treatment Arm:
      1. Anti-microbial TheraGauze (TheraGauze/tobramycin)
      2. Iodoform wick/ plain cotton wick
    - Length of packing used (mm)
  - Laboratory Assessments – Per standard clinical care the abscess contents will be sent for routine Gram stain, bacterial culture and susceptibility testing as dictated by the patient's insurance and ED policy.
    - Obtain results when available
  - If patient is to receive iodoform wick/plain cotton wick then the care provider will have the option of prescribing a p.o. antibiotic, as is frequently done in these clinical settings. The following oral antibiotic choices are available for subjects in the control arm only:
    - Bactrim (TMP/SMX)
    - Vibramycin (doxycycline)
    - Cleocin (clindamycin)

Phone Follow up Contact Day 2 (+2)

Return visit reminder and wound status follow up performed by Sentara Study Coordinator.

- Questions
  - Fever since leaving ED? (y/n, record temp if taken)
  - If prescribed, was antibiotic prescription filled (y/n)
  - If prescribed, has antibiotic been taken (y/n, # doses)
  - If antibiotics taken, were any side-effects noted (y/n, list)
  - Increased or decreased pain (y/n, increased/decreased)
  - Increased or decreased size of redness (y/n, increased/decreased)
  - Any new symptoms? (y/n, list) Specific questions will include: presence of rash, loose stool, nausea, vomiting, abdominal discomfort, headache, dizziness, drowsiness, thrush, as well as any change in local signs or symptoms including pain and redness, new skin lesions, enlarged lymph nodes, and sore or white spots in the mouth.

Visit 2 - Day 3 -1/+2: (ED)

Subjects' wound status will be evaluated. The following information will be collected and recorded on a hard copy Case Report Form at this visit:

- Questions about infection
  - Infection overall (better/same/worse)
  - Fever > 38°C at home since incision? (y/n)
  - Persistent discharge (y/n)
  - Pain (increased/same/decreased/resolved)
  - Medical evaluation between day 1 and day 3 visit (y/n)
  - New lesions (y/n)
  - Was an p.o. antibiotic prescribed (y/n)
    - If yes, was the prescription filled (y/n)
    - How many doses have been taken so far? (##)
  - Any diarrhea? (y/n)
  - Any nausea or vomiting? (y/n)
  - Any abdominal discomfort? (y/n)
  - Any new rash? (y/n)
  - Any other new symptoms including headache, dizziness, drowsiness, thrush, as well as any change in local symptoms.
  -
- Bacterial burden in wound bed – Wound culture performed using quantitative methods for culturing wound base (Gardner, Frantz et al. 2006). Cultures taken to [name] lab for quantitation, swab may be stored at 4°C, if obtained after business hours.
  - Quantitation of bacteria present (colony counts performed in [name] lab)
  - Speciation of bacteria present (CHKD clinical microbiology laboratory using CLSI standards)
  - Antibiotic susceptibility testing of bacteria present (CHKD clinical microbiology laboratory using CLSI standards)
- Wound assessment
  - Fever > 38°C in ED? (y/n, record temp)
  - Packing present (y/n)
  - Erythema at widest diameter (mm)

- Abscess induration at widest diameter (mm)
    - Tenderness around the wound? (y/n)
    - Removal of packing
    - Does wound require repacking? (y/n)
- Clinical Options
  - Return to ED for additional clinical evaluation and management (y/n)
      - Reason for reevaluation (infxn worsening/infxn non-improvement/other)
      - Another incision and drainage in the ED (y/n)
      - Addition of oral antibiotics (y/n)
      - Admission for i.v. Abx (y/n)
      - Admission for surgical intervention (y/n)
      - Return to ED in 2 more days (y/n)
- Schedule follow-up visit in Infectious Diseases Clinic at Children's Hospital of The King's Daughters (CHKD) in  $5 \pm 2$  days

Phone Follow up Contact Day Prior to CHKD visit:

Return visit reminder performed by Study Coordinator.

- Fever since leaving ED? (y/n, record temp if taken)
  - If prescribed, has antibiotic been taken (y/n, # doses)
  - If antibiotics taken, were any side-effects noted (y/n, list)
  - Increased or decreased pain (y/n, increased/decreased)
  - Increased or decreased size of redness (y/n, increased/decreased)
  - Any new symptoms? (y/n, list) Specific questions will include: presence of rash, loose stool, nausea, vomiting, abdominal discomfort, headache, dizziness, drowsiness, thrush, as well as any change in local signs or symptoms including pain and redness, new skin lesions, enlarged lymph nodes, and sore or white spots in the mouth.

Visit 3 - Day  $7 \pm 2$ : (CHKD Infectious Diseases Clinic):

Follow up on subjects' wound status. The following information will be collected and recorded on a hard copy Case Report Form at this contact.

- Questions about infection
  - Fever  $> 38^{\circ}\text{C}$  at home since incision? (y/n)
  - Pain (increased/same/decreased/resolved)
  - Redness (increased/same/decreased/resolved)
  - Persistent discharge (y/n)
  - Wound size (increased/same/decreased/resolved)
    - If resolved, day of wound closure (day)
  - New lesions since day 3 visit (y/n)
  - Was an p.o. antibiotic prescribed (y/n)
    - If yes, was the prescription filled (y/n)
    - How many doses have been taken so far? (##)
  - Any diarrhea? (y/n)
  - Any nausea or vomiting? (y/n)
  - Any abdominal discomfort? (y/n)
  - Any new rash? (y/n)

- Any other new symptoms including headache, dizziness, drowsiness, thrush, as well as any change in local symptoms.
- Wound assessment
  - Fever > 38°C in CRU? (y/n, record temp)
  - Packing present (y/n)
  - Diameter of erythema (mm) at widest diameter
  - Diameter of wound (mm) at widest diameter
  - Tenderness around the wound? (y/n)
- Clinical Assessment (decided by PI or sub-I)
  - Infection worsening, non-improvement, improvement
- Clinical Options (decided by PI or sub-I)
  - No follow-up needed unless infection worsens
  - Suggest follow-up
- Clinical Follow-up, if applicable (obtained from subject or medical record after follow-up)
  - Another incision and drainage in the ED (y/n)
  - Addition of oral antibiotics (y/n)
  - Admission for i.v. Abx (y/n)
  - Admission for surgical intervention (y/n)
  - Return to ED in 2 more days (y/n)

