In 2003 Simplex P with tobramycin was the first FDA approved antibiotic impregnated bone cement ([www.stryker.com](http://www.stryker.com)). Preparations of tobramycin-impregnated bone cement appear to generally range from 1g to 1.2g in 20 ml (50 – 60 mg/ml) (Sterling, Crawford et al. 2003, McLaren, McLaren et al. 2008). Tobramycin is reported to be the antibiotic of choice for bone cement for more than 75% of orthopedic surgeons (Fish, Hoffman et al. 1992) with excellent local tobramycin levels and minimal systemic tobramycin levels (Soto-Hall, Saenz et al. 1983, Eckman, Henry et al. 1988, Davies and Harris 1991, Pritchett and Bortel 1992, Brien, Salvati et al. 1993, Sterling, Crawford et al. 2003, McKee, Li-Bland et al. 2010). Despite the extensive literature on tobramycin bone cement there are no mentions of local toxicity. It is notable that so little toxicity has been reported given the significantly varying amounts of tobramycin cement are used for different types of orthopedic procedures and depending on the amount of bone being replaced. The wounds the tobramycin cement are in deep tissue spaces that are highly vascular. In contrast, TheraGauze/tobramycin will be placed into small (2 - 10ml) cutaneous abscesses where the bacterial infection has been walled off to protect the body from spread.

Tobramycin has also been used as a topical ophthalmic preparation for many years both as an ointment and drops (3 mg/ml) (e.g., Tobrex). Despite the very sensitive nature of topical application to the eye the package insert for Tobrex notes <1% hypersensitivity and eye or eyelid irritation is 3%, which is a typical rate for antibiotic eye drops. Additionally, Tobramycin eye drops (3 mg/ml) have been shown to have no adverse effects on reepithelialization and be well tolerated after penetrating keratoplasty (Blavin, Sauer et al. 2012)

Thus, there are several decades of human data demonstrating the safety of tobramycin when used topically for cutaneous and ocular wounds and in surgical wounds. The data suggests that local or systemic toxicity is extremely rare when tobramycin is used in these ways.

**Primary Endpoint.** The primary endpoint of the study is to evaluate the safety of and identify side effects of TheraGauze/tobramycin wound packing compared with standard of care management for cutaneous abscesses requiring incision and drainage.

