#### **STATISTICAL ANALYSIS PLAN**

The research coordinators will collect data on a hard copy source document. Clinical and laboratory data will then be entered into an Access database by the coordinator and lab personnel.

The data will be analyzed using SAS 9.4 software. All statistical tests will be two-sided with a significance level of 0.05. Patients who withdraw while on treatment will be included in the data analysis for each time point before withdrawal. Baseline and follow-up measurements of safety, tolerability, numbers of pathogenic bacteria, wound infection persistence or worsening, and gross effects on the rate of wound healing will be summarized using descriptive statistics such as mean, median, standard deviation, interquartile range, frequency, and percentage where appropriate. Normality assessments for the continuous variables will be completed using Shapiro-Wilk tests and stem-and-leaf plots.

Tests of equivalence between the TheraGauze + tobramycin and standard iodoform wick packing treatment groups will establish statistical significance if the two-sided 90% confidence

interval for the difference falls within the limits  $(-\delta, \delta)$ , where  $\delta$  is the margin of clinically accepted difference. This analysis will determine whether the outcomes are equivalent between the TheraGauze+tobramycin and standard iodoform wick packing treatment groups.

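### Visits 2 and 3 ask about diarrhea, nausea/vomiting and abdominal discomfort without limiting them to new onset, and Visit 1 lists no matching baseline items, so symptoms present before treatment may be counted as side effects

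*Combined protocol and SAP*

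**What the plan says.** The protocol's Primary Endpoint section states: "The primary endpoint of the study is to evaluate the safety of and identify side effects of TheraGauze/tobramycin wound packing", compared with standard of care. Symptom reports are therefore the main data.

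**Follow-up forms** (Study Treatments, Visits 2 and 3, Questions about infection). The nausea item reads "Any nausea or vomiting? (y/n". Diarrhea and abdominal discomfort have the same form. The items that follow, on rash and on other symptoms such as headache and dizziness, are limited to new events. Both telephone contacts also ask for new symptoms, with loose stool, nausea, vomiting and abdominal discomfort among the prompts.

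**Entry form** (Visit 1). The block headed "Characteristics of symptoms and history" starts with "Duration of symptoms (number of days" and then covers fever, drainage, and personal and family abscess history. Elsewhere the form records chronic conditions, concomitant medications, allergies and abscess dimensions. The Study Visit Schedule ticks a row for history and present symptoms at Visit 1 but does not define its content.

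**Eligibility** (Subject Eligibility). Inclusion allows "No or mild fever" up to 38.5 °C. The nearest exclusion is "Systemic illness or deep-seated infection requiring inpatient admission (i.e. hypotension, tachycardia, or tachypnea". No criterion names current nausea, diarrhea, abdominal discomfort, headache or rash.

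**SAP.** The data to be summarised begin with "Baseline and follow-up measurements of safety, tolerability, numbers of pathogenic bacteria, wound infection persistence or worsening".

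**The concern.** A yes to an unrestricted question at Day 3 or Day 7 can mean that the symptom began after treatment, or that the subject arrived with it. The listed Visit 1 data do not separate the two.

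This touches the comparison the trial is built on. The Background section names diarrhea and nausea among the common effects of the oral antibiotics, and the protocol presents avoiding such effects as the main likely benefit of the packing. The three unrestricted items cover these symptoms. Carried-over symptoms raise the apparent rate in both arms, and they make up the larger share of reports in whichever arm has fewer true events.

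The plan is also incomplete on its own terms. It promises a baseline summary of safety and tolerability, but no listed item supplies one for gastrointestinal symptoms, rash or headache.

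**Working it through.** **1. What each item can distinguish**

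| Symptom | Visit 1 item listed | Visits 2 and 3 | Telephone contacts |
|---|---|---|---|
| Diarrhea / loose stool | none | any | new |
| Nausea or vomiting | none | any | new |
| Abdominal discomfort | none | any | new |
| Rash | none | new | new |
| Headache, dizziness, drowsiness, thrush | none | new | new |

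The full problem is in the first three rows. In the last two, the only weakness is that newness rests on the subject's recall and cannot be checked against an entry record.

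**2. Sample size**

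Study Size gives 100 randomized, 50% retention and a 2:1 ratio. Completers = 100 × 0.50 = 50, which reproduces the stated 50. At 2:1 this is about 33 TheraGauze and 17 control.

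**3. Effect on the rates for one unrestricted item**

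Inputs:
- p, the true new-onset rate. Assumed 20% in controls, which is the Background's approximate antibiotic diarrhea figure. It is an upper case, because antibiotics are optional in that arm. Assumed 5% with TheraGauze; this figure is not in the documents.
- b, the share of subjects who have the symptom at entry and still report it at follow-up. Not in the documents; shown from 0 to 20% and taken as equal in both arms.

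Observed rate = b + (1 - b)p. Observed difference = (1 - b) × (0.20 - 0.05).

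| b | Control | TheraGauze | Difference (points) | Half-width of 90% interval (points) |
|---|---|---|---|---|
| 0 | 20.0% | 5.0% | 15.0 | 17.1 |
| 5% | 24.0% | 9.8% | 14.3 | 19.0 |
| 10% | 28.0% | 14.5% | 13.5 | 20.6 |
| 20% | 36.0% | 24.0% | 12.0 | 22.7 |

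The half-width is 1.645 × √[pC(1 - pC)/17 + pT(1 - pT)/33], using the observed rates.

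At b = 10%, the expected carried-over answers are 33 × 0.10 = 3.3 in the TheraGauze arm and 17 × 0.10 = 1.7 in the control arm. They make up 0.10/0.145 = 69% of TheraGauze yes answers and 0.10/0.28 = 36% of control yes answers. Power to detect the difference with a two-sided 5% test is about 40% at b = 0, 29% at 5%, 22% at 10% and 15% at 20%.

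**4. If b differs between arms**

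With 10% in controls and 5% in TheraGauze, the observed difference is 28.0 - 9.75 = 18.25 points. With the shares reversed it is 24.0 - 14.5 = 9.5 points. Without baseline items, nobody can tell which case applies.

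**The case against.** The strongest reply is that the plan has other safeguards, and that the effect is small for a pilot analysed largely by description.

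- **Telephone contacts.** They ask about the same gastrointestinal symptoms as new events, before each visit. This is a real mitigation for subjects who are reached. It still depends on recall, and no rule says which source prevails when a call and a visit form disagree.
- **Causality assessment.** The PI judges every adverse event, and can answer no for lack of a temporal relationship or because of concurrent disease. That filter exists. But the forms collect no onset date for it to use, and the question concerns only the study drug. Not having taken the study drug is itself a ground for a no, so on a plain reading the filter cannot yield a comparable rate in the control arm.
- **The visit schedule row.** It may have been meant to capture current symptoms at Visit 1. Its content is undefined, so it can neither be credited nor dismissed.
- **Other exclusions and baseline measures.** Recent antibiotics, inflammatory bowel disease and pregnancy are excluded, which lowers b. Temperature, erythema and induration are measured at Visit 1, so increasing redness, one of the local-toxicity signs, does have a baseline. Both points stand.
- **Size.** Under equal b the difference moves by only 0.7 to 3.0 points, well inside the interval half-width of 17 points or more. This also stands.

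A reader might infer that headache and rash present at entry are counted in the same way. They are not: the follow-up items for these ask only about new events.

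**Conclusion.** The gap is real and confined mainly to three items. Gastrointestinal symptoms that predate treatment may be counted as side effects, and the promised baseline summary lacks gastrointestinal, rash and headache data. Under the assumptions in the working, both arms' rates are inflated and the difference falls from 15.0 to between 14.3 and 12.0 points for b of 5% to 20%. The figures illustrate the mechanism; b and the 5% TheraGauze rate are assumptions, and the formula takes every counted entry symptom to persist until follow-up.

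Three stronger readings are not supported:

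- **That these symptoms will be counted and cannot be removed.** The plan has no rule turning yes/no answers into side-effect counts, so only the possibility follows.
- **That the TheraGauze rate is overstated by a particular multiple.** Any such multiple depends on the assumed 5% and the assumed b.
- **That the pull toward zero makes a false finding of equivalence easier.** The SAP gives its margin no number, and at this size the interval widens as the difference shrinks. The outer limit goes from 15.0 + 17.1 = 32.1 points at b = 0 to 13.5 + 20.6 = 34.1 at b = 10%. With equal b, the error by itself favours neither arm.

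The change is worth making because it is cheap and because baseline symptoms not recorded at entry are hard to reconstruct reliably.

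**What to change.** 1. At Visit 1, after consent and before randomization, ask the symptom items used on the Day 2 call, each with a mild, moderate or severe grade on the protocol's own adverse event severity scale. A bare yes/no baseline could not show worsening later.
2. At Visits 2 and 3, reword the diarrhea, nausea/vomiting and abdominal discomfort items to ask for symptoms new or worse since Day 1. Record the onset date, and grade yes answers on the same scale.
3. State in the SAP that a side effect is counted, in both arms alike, only if the symptom was absent at Visit 1 or has worsened since.
4. Define the schedule's Visit 1 symptom row as this checklist.

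Rewording the three items alone would close much of the gap, but it would still rest on recall and leave the baseline summary empty.

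The cost is about a dozen short items, an estimated two minutes per subject (100 × 2 = 200 minutes over the trial), and one SAP sentence. The downside is that a symptom already present at entry counts only if it worsens. No treatment procedure changes.
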